4.1. Sample Size

Data from the initial 20 LRG subjects will be evaluated by the DSMB to ensure pharmacodynamic activity before the remainder of the LRG is enrolled. The size of this group was determined by non-statistical reasons.

Safety and pharmacodynamic data from the entire LRG will be reviewed by the DSMB to ensure safety and pharmacodynamic adequacy. The size of the LRG is 80 subjects. Up to 45 LRG subjects will have received SYN023. This number was judged adequate to give a preliminary assessment of study drug performance in the LRG.

Three hundred and twenty patients are required in the Per-protocol Population to satisfy the efficacy elements of the AUEC₁₋₁₅ secondary endpoint. Synermore anticipates a total size of 368 subjects to be enrolled to NRG to allow a reasonable rate of loss to follow-up and exclusions. Since PEP should not be delayed and some inclusion/exclusion criteria may not be known at the time of randomization some subjects may be excluded (but not replaced) from the Per-protocol Population by the Per-Protocol Adjudication Board if they are later discovered to have met an exclusion criterion.

Detailed sample size considerations can be found in protocol Section 7.8 for full iterations.

Randomization will be adjusted by the randomization center such that patients are proportionately distributed between the trial sites and patients with wounds of the head, neck or genitalia are stratified approximately equally into the treatment groups.

Table 4.1-1 Sample Sizes by Risk Group and Treatment

Group	Enrollment	Treatment	Protocol version	Rabies Vaccination	Number of subjects
LRG	initial	HRIG 20 IU/kg	2.0	Study Days 1, 4, 8, 15	5
LRG	initial	SYN023 0.3 mg/kg	2.0	Study Days 1, 4, 8, 15	15
LRG	general	HRIG 20 IU/kg	3.0	Study Days 1, 4, 8, 15, 29	30

Group	Enrollment	Treatment	Protocol version	Rabies Vaccination	Number of subjects
LRG	general	SYN023 0.3 mg/kg	3.0	Study Days 1, 4, 8, 15, 29	30
NRG	general	HRIG 20 IU/kg	3.0	Study Days 1, 4, 8, 15, 29	184
NRG	general	SYN023 0.3 mg/kg	3.0	Study Days 1, 4, 8, 15, 29	184
Total required for initial LRG enrollment					20
Total required for general LRG enrollment					60
Total required for NRG enrollment					368
Total maximum enrollment					448

4.2. Randomization, Stratification, and Blinding

Subjects will not be replaced after randomization. They may be excluded from the Per-protocol Population. Allocation of randomization among sites will be adjusted to accommodate stratification of head, neck or genitalia bites or site enrollment imbalances.

4.2.1. LRG Initial Enrollment Randomization

Subjects in the initial enrollment group will be randomized on a 3:1 basis to treatment with SYN023 or HRIG. Eligibility for the LRG subjects is described in Protocol Section 2.2.1. The group as described in Table 4.1-1 is randomized in a 3:1 ratio. Subjects in the initial LRG may be excluded from LRG the Per-protocol Population but they will not be replaced.

4.2.2. LRG and NRG General Enrollment Randomization

Subjects in the general enrollment of LRG and NRG will be randomized on a 1:1 basis within each group to treatment with SYN023 or HRIG. Subjects will be allocated to treatment sites to approximate the ratio in Table 4.1-1. Within NRG enrollment subjects with head or neck bites or bites to genitalia will be stratified on a 1:1 basis into SYN023 or HRIG treatment groups.

Study sites wishing to randomize a subject will contact the study randomization center either telephonically or by electronic means. The study randomization center will determine the randomization allocation and return the randomization assignment in written communication to the study site.

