5.2. Protocol Deviations

All protocol deviations (including violations) will be assessed and reviewed at the BDRM prior to the database lock. Any exclusion of randomized subjects from the Per-protocol Population after randomization must be made by the Per-protocol Adjudication Board. Subjects with the following significant deviations will be excluded from the Per-protocol Populations:

- Defective informed consent
- Received the incorrect study drug
- Received the incorrect dose ($\pm 20\%$) of study drug
- Failed to complete the scheduled rabies vaccinations through Study Day 29
- Are discovered to lack adequate prophylactic treatment of all exposure sites
- Are discovered to be injured by animal other than those listed
- Are discovered to have an interval >54 hours from rabies exposure to the start of prophylaxis
- Are discovered to have RVNA ≥ 0.1 IU in serum obtained at Study Day 1
- Receive prohibited treatment during the trial
- Are found not to have a modified WHO Category 3 exposure
- Are discovered to have or have developed HIV infection or other immunodeficiency state
- Second high-risk animal bite or contact requiring PEP

As the study is ongoing, additional significant protocol deviations can also be identified or defined by the Per-protocol Adjudication Board. The list of significant protocol deviations can be updated accordingly.

Significant deviations categorized according to the list will be summarized in a table for the As-treated Population. All protocol deviations will be presented in a listing and an additional listing

of deviations for the randomized subjects who missed any dose of study drug or rabies vaccine will be provided.

6. Demographics and Baseline Characteristics

Demographic parameters (age, gender, race and ethnicity), randomization factors (including study site and bite location) and other baseline characteristics will be summarized by treatment group for all subjects in the As-treated Population. The summary can be used to check potential imbalance between treatment groups.

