8.1.1. Primary Analysis

8.1.1.1. Superiority Testing on Study Day 8

The first element is superiority of the geometric mean concentration of RVNA (serum) in SYN023 recipients on Study Day 8. RVNA was selected because it is a generally accepted surrogate for rabies vaccine protection. If it is possible to demonstrate quicker and higher concentrations in the blood of RVNA from SYN023 then this may be evidence of greater potency and perhaps effectiveness.

GMC for a group of subjects is calculated by multiplying all values and taking the n th root of this number, where n is the number of subjects with available data. Because concentrations are often approximately log-normally distributed, they are customarily analyzed on a logarithmic (log) scale; a difference in arithmetic means (Δ) on a log scale becomes a ratio of geometric means (\emptyset) when the results of analysis are converted back to the original data scale. Thus, each hypothesis is a statement regarding \emptyset . The alternative hypothesis (H_a) is that the SYN023 vaccine is superior to HRIG.

$$H_a: \emptyset = \frac{GMC_{SYN023}}{GMC_{HRIG}} > 1$$

The null hypothesis is the complement of the alternative, meaning that the SYN023 vaccine is inferior or equal to HRIG.

$$H_0: \emptyset = \frac{GMC_{SYN023}}{GMC_{HRIG}} \leq 1$$

The null hypothesis will be rejected at a significance level of 2.5% ($\alpha = 0.025$) if the lower bound of the one-sided 97.5% confidence interval (CI) for the GMC ratio is greater than 1.

In the summary table, by-treatment GMCs and geometric standard deviations (Geo SDs) will be displayed, where Geo SD is calculated by converting the normal concentration values in to log-normal values, calculating the typical standard deviation of log transformed concentrations and then taking its antilog for the geometric standard deviation. GM ratio along with its coefficient of variation (CV) and 95% CI will also be displayed in the summary table.

8.1.1.2. Non-inferiority Testing on Study Day 99

The second element is immune response to the rabies vaccine on Study Day 99 measured by the noninferiority of the Study Day 99 GMC of RVNA in SYN023 recipients compared to Study Day 99 GMC of RVNA in the HRIG recipients. Synermore defines non-inferiority rabies vaccine response as a 20% margin of non-inferiority and equal allowance (number of subjects in SYN023 = number of subjects in HRIG) and alpha is taken to be 0.025.

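### NRG allocation uses bite location and site, but the planned tests leave both out; adjusting for them is a free, modest gain in precision

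*SAP*

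**What the plan says.** **Allocation.** SAP 4.2.2 (and protocol 2.6.2) states that NRG subjects bitten on the head, neck or genitals "will be stratified on a 1:1 basis into SYN023 or HRIG treatment groups". SAP 4.2 adds: "Allocation of randomization among sites will be adjusted to accommodate stratification of head, neck or genitalia bites or site enrollment imbalances". Protocol 7.2 repeats that randomization is adjusted to keep the stratification and the site allocation. Protocol 3.2.8 sends per-protocol exclusions back to the enrollment center for the same purpose.

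**Use of the factors.** SAP Section 6 lists "randomization factors (including study site and bite location") among the items in the baseline table and says of that table: "The summary can be used to check potential imbalance between treatment groups". No other use is stated.

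**Analyses.**
- Day 8 and Day 99 GMC ratios (SAP 8.1.1.1 and 8.1.1.2): a difference in mean log RVNA converted back to a ratio, judged by the "lower bound of the one-sided 97.5% confidence interval". The stated reason for the log scale is "Because concentrations are often approximately log-normally distributed, they are customarily analyzed on a logarithmic (log) scale". There is no stratum or site term.
- Day 99 responder rate (SAP 8.1.1.3): Pearson chi-square or Fisher's exact test with Newcombe/Wilson-type limits, unstratified.
- Rabies cases (SAP 8.1.1.4): a count, with no comparison between arms.
- Day 4 and AUEC1-15 (SAP 8.2): presented as in 8.1.1.1.
- Sensitivity (SAP 8.1.2): the same analyses in the As-treated Population.

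Protocol 7.3 and 7.8 contain no covariate term either.

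**The concern.** When allocation is balanced on a factor, the variation due to that factor drops out of the treatment contrast. An unadjusted standard error still counts it. If the factor predicts RVNA, the interval is then wider than the design warrants and the test runs below its nominal 2.5%. What is at stake is some precision, available at no extra cost because both factors are already recorded.

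Two features of the plan add to the case. The primary analysis is per-protocol, and protocol 2.3 allows for about 15% (48 patients) of loss and exclusions, so the balance achieved at randomization may be disturbed. The SAP also states no remedy if the baseline table shows imbalance, and an adjustment chosen after seeing that table would be data-driven.

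**Working it through.** **1. The plan's own figure.** Protocol 7.8.4 sizes the NRG on AUEC1-15: true ratio 1.45, margin 1.10, CV 108.78%, one-sided alpha 0.025, power 80%.

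- Log SD = √ln(1 + 1.0878²) = 0.884.
- n per arm = 2 × 0.884² × (1.960 + 0.842)² / [ln(1.45/1.10)]², which rounds up to 161, or 322 in total.

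The stated 320 is reproduced by an unstratified two-group formula. The planned analysis therefore agrees with the sample-size calculation; it differs only from the randomization.

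**2. Effect of adjustment.** Let R² be the share of log-RVNA variance explained by bite stratum and site. The documents give no value, so 0 to 0.20 is an assumed range.

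- Half-width, adjusted over unadjusted: √(1 − R²).
- Actual one-sided error of the unadjusted limit, with arms balanced within the factors: 1 − Φ(1.96/√(1 − R²)).
- AUEC1-15 power at 160 per arm: Φ(ln(1.45/1.10) / [0.884 × √((1 − R²) × 2/160)] − 1.96).
- Day 99 lower limit at an observed ratio of 0.88 with an assumed log SD of 1.0: 0.88 × exp(−1.96 × √((1 − R²) × 2/160)).

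| R² | Half-width factor | One-sided error, unadjusted | AUEC1-15 power, adjusted | Day 99 lower limit |
|---|---|---|---|---|
| 0 | 1.000 | 2.50% | 79.8% | 0.707 |
| 0.05 | 0.975 | 2.22% | 81.8% | 0.711 |
| 0.10 | 0.949 | 1.94% | 83.8% | 0.715 |
| 0.20 | 0.894 | 1.42% | 87.8% | 0.723 |

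A simulation agrees. It used 320 subjects, six sites, a 10% bite stratum, permuted blocks of four and 10,000 runs per setting; these design values are assumptions. The unadjusted error was 2.4, 2.2, 1.8 and 1.6%, and the adjusted error stayed at 2.4 to 2.5%. At R² = 0 the two standard errors were practically equal (ratio 1.0005), so adjusting costs almost nothing if the factors turn out to be irrelevant.

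The AUEC1-15 column uses the protocol's 1.10 margin. SAP 8.2 states no margin and points to 8.1.1.1, which tests against 1. Against 1, unadjusted power is already Φ(ln 1.45/[0.884 × √(2/160)] − 1.96), about 96%, and less is left to gain.

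**3. Where the gain could change a conclusion.**
- Day 8: protocol Table 7.8-1 assumes a ratio above 10 and needs fewer than 10 subjects. No effect.
- Responder rate: protocol Table 7.8.3-2 needs 32 to 72 subjects in total. No effect of note.
- Day 99 GMC: the historical intervals in protocol Table 7.8.2-1 imply log SDs of about 0.83 to 1.16 at Days 84 and 112, hence the assumed 1.0. Power at a true ratio of 0.88 moves only from about 13% to 16% at R² = 0.20. For an observed 0.88 to clear 0.8, √(1 − R²) must fall to ln(0.88/0.8)/(1.96 × √(2/160)) = 0.435, so R² would have to be about 0.81. With the protocol's stated CV of 17% instead, the log SD is 0.169 and the unadjusted lower limit is 0.88 × exp(−1.96 × 0.169 × √(2/160)) = 0.85, which already passes. Adjustment is not decisive on either reading.
- AUEC1-15: the one test with visible room.

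**The case against.** The case for leaving the plan alone is substantial.

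- *Direction.* The unadjusted limits can only be too wide. The false-positive rate is not inflated, and the analysis is consistent with the sample-size formulas. This stands.
- *Site balance is not clearly stated.* SAP 4.1 and 4.2.2 can be read as spreading enrollment across sites, not as balancing arms within each site, and protocol 3.3 says the randomization procedure was not yet available. If arms are not balanced within site, the unadjusted interval is correctly calibrated for that factor. This stands. Adjustment would still remove site variance from the residual, so there is still precision to gain.
- *Neither factor is shown to predict RVNA.* Protocol 1.6 and 3.9.5 tie bite location to the risk of rabies transmission, not to serum titers. Protocol Section 4 describes the two vaccine brands as the same product. HRIG is dosed at 20 IU/kg from either preparation. The switch of preparation happens over time within a site and concerns the HRIG arm only, so a site term would capture it poorly. This stands and leaves R² an open assumption.
- *A stratified responder analysis could do harm.* Historical response was 100% in both arms at Day 84, and 95.9% (SYN023) and 98.7% (HRIG) at Day 112. The usual variance of a Mantel-Haenszel ratio is zero in any stratum where everyone responds, so an interval over bite-by-site cells can collapse. The planned score-type limits remain usable. This stands and shapes the fix.

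These points limit the size of the gain. None gives a reason for leaving out factors the trial already allocates by and records.

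**Conclusion.** The SAP names bite location and site as randomization factors and then uses neither in the three inferential primary elements or in the Day 4 and AUEC1-15 tests. The planned tests remain valid. The possible loss is precision: half-widths 0 to about 11% longer than needed for R² between 0 and 0.20, and AUEC1-15 power of about 80% where 82 to 88% might be had at R² of 0.05 to 0.20. This rests on an assumed R², on 160 per arm, on the protocol's AUEC1-15 inputs and, for the claim that limits are too wide, on arms being balanced within the factors.

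A reader might infer three stronger things that the documents do not support:
- That the confidence limits are wrong for the design. They are at worst conservative, and at R² = 0 they are the same.
- That every primary element is affected. The rabies element is a count with nothing to adjust.
- That adjustment would secure Day 99 GMC non-inferiority. With a log SD near 1.0, the lower limit at an observed 0.88 stays near 0.71 to 0.72 against a bound of 0.8.

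This is a free improvement of minor priority.

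**What to change.** Before unblinding:

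- **SAP 8.1.1.1, 8.1.1.2 and 8.2.** Estimate the Day 8, Day 99, Day 4 and AUEC1-15 ratios from a linear model on the log scale with treatment, bite stratum (head/neck/genital or other) and site. Pool small sites by a prespecified rule, for example by country. Back-transform the treatment estimate and its limits. Keep the unadjusted ratio as a sensitivity analysis.
- **SAP 8.1.1.3.** Keep a score-type interval that stays usable near 100% response. Stratify it by bite location only if the strata are not sparse, with the sparseness rule written in advance. Do not use a Mantel-Haenszel ratio over bite-by-site cells.
- **SAP 4.2.** State whether arms are balanced within site or only enrollment is spread across sites.

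The cost is SAP wording and minor programming; both factors are already collected. A model statement is needed in any case, because SAP 8.1.1.1 does not say how the interval for the GMC ratio is computed and Appendix 15.2 gives only a single-group interval. Protocol 7.9.2 allows such additions through the SAP.

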4.2.3. Blinding and Unblinding

The LRG and the NRG are both blinded until Study Day 365. If the last subject in LRG reaches Study Day 365 even if the NRG is still in progress, then the LRG group may be unblinded. The NRG group will remain blinded until Study Day 365. The DSMB will conduct unblinded analyses before Study Day 365 as specified by the protocol and inform the sponsor of the overall results of those analyses. The purpose of these analyses is to permit advancement of the study and to inform the sponsor of the status of certain endpoint elements so that the sponsor may

make product development decisions. Since investigational agent will have been delivered, still blinded specimens for analysis collected and individual treatment assignments still unknown to the sponsor, this should not affect the conduct of the trial during the observation period required for clinical rabies surveillance.

The site's investigational pharmacist or product manager (or designee) will need to be unblinded in order to manage study drug inventory and prepare doses. Other unblinded persons on the study are the unblinded study monitor that will need to audit study drug stocks and the study monitor(s). All unblinded persons must take care to not reveal individual subject treatment regimen assignments to any other member of the study team.

The investigational pharmacist or product manager must be a designated study team member who is not an employee of the sponsor and who will have no other clinical or regulatory responsibilities associated with the conduct of the study during the entire study period. Unblinded study personnel must not participate in the evaluation of AEs. A Delegation of Authority Log will be maintained by the site and will identify the individual(s) authorized to function as the study drug manager, i.e., individuals with access to study blinding information.

Labels accompanying the syringes of prepared study drug will not indicate which study drug is in the syringe but will only contain the study identification and subject ID number. Identical syringes and needles will be used for preparation and administration of each study drug.

If there is an urgent clinical requirement to know a subject's treatment assignment, the investigator (in consultation with the medical monitor, if possible) will make a written request to the investigational pharmacist or product manager for urgent unblinding of a subject's treatment. The request must include the subject ID number, the date, a brief justification of the clinical requirement to the study drug manager in the research pharmacy, and the investigator's signature. The request will be kept in the study file.

Upon receipt of proper written request, the investigational pharmacist or product manager will disclose the treatment group to the investigator. The sponsor must be notified immediately of any clinically required break of the study blind on an Immediately Reportable Event Form.

4.3. Analysis Set

The Per-protocol Adjudication Board will review blinded data and decide whether to exclude a subject from the Per-protocol Populations before each DSMB meeting. All analysis set definitions should be finalized prior to final study unblinding or through thorough review in the Blinded Data Review Meeting (BDRM). The list of major protocol deviations must be finalized prior to the database lock and unblinding.

Primary analyses will be performed on the Per-protocol Populations. The As-treated Population will be applied on the primary endpoints as sensitivity analyses.

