- In Synermore's experience about 2% to 5% of subjects may have evidence of unknown or unrecalled rabies vaccination. Their RVNA response may be much quicker and higher than in naïve patients. Since the RVNA is a crucial efficacy element these subjects with a RVNA ≥ 0.1 IU that is taken to be evidence of previous vaccination must be analyzed differently.
- Subjects will be excluded for conditions discovered after randomization that impair protection such as immunodeficiency.
- Subjects will be excluded if excessive treatment delay (>54 hours) is discovered.
- Subjects will be excluded if they receive or have received protocol prohibited treatments such as RIG that will confound analysis.
- Subjects will be excluded if all of the bite wounds are discovered to have not been properly treated or injected.
- Subjects will be excluded if bites are determined to be due to non-protocol listed animals
- Subjects will be excluded if they leave the trial or their status is unknown.

Rationale for bite, broken skin lick and broken skin scratch exposure injuries eligibility for trial
Individuals with WHO Category III rabies exposures with some exceptions are eligible for the trial since they are considered WHO Category 3 exposures and RIG is indicated for these exposures. WHO Category 3 exposures include single or multiple transdermal bites or scratches or licks on broken skin, mucous membrane saliva contamination and unprotected bat exposures. Depending on the protocol defined risk substratum all observed bites, broken skin scratches and broken skin licks unprotected bat contacts and saliva contamination of mouth nose and eyes are eligible for the trial.

Rationale for bite-to-treatment interval

The bite-to-treatment interval for the administration of RIG is recommended to be as soon as possible up to 7 days by the WHO (WHO 2013). This judgment reflects the emergence of naturally produced antibodies at about 7 days. A number of surveys report that rabies cases were rare when treatment was instituted within 2 to 3 days (Si et al. 2008, Quiambao et al. 2009).

Animal studies suggest that rabies virus may enter nerves within hours (Watson et al. 1981).

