Day 112	73	1.43	(1.09, 1.87)	76	1.71	(1.38, 2.11)

Non-Inferiority test for ratio of two geometric means is used for determining the sample size. The null hypothesis is that the ratio for the two treatments is less than the defined margin which is expressed as:

$$H_0: \emptyset \leq \emptyset_L \text{ where } \emptyset_L < 1$$

The alternative hypothesis for superiority is $H_1: \emptyset > \emptyset_L$. The calculated ratio between SYN023/RIG and the 95% confidence intervals for the ratio are presented in Table 7.8.2-2 and were used as inputs for the sample size calculation in PASS 15 software.

Table 7.8.2-2: Ratio (SYN023/HRIG) and 95% Geometric Confidence Intervals for Each Time-point for RVNA from SYN023-002 Protocol, Historical Data

Time Point	Ratio (SYN023/HRIG) for RVNA- SYN023-002	95% Geometric Means Ratio CI		CV
Day 35	81.28%	62.19%	106.23%	13.59%
Day 42	88.94%	68.79%	114.99%	13.04%
Day 84	88.50%	64.04%	122.30%	16.47%
Day 112	86.94%	61.88%	122.15%	17.32%

The sample size is calculated at 80% power with 20% margin of non-inferiority and equal allowance (number of subjects in group 1 = number of subjects in group 2) and alpha is taken to be 0.025.

The non-inferiority of serum GMC RVNA on study day 84 in SYN023 recipients (above) with respect to HRIG recipients would require the sample size of 138 for 80% power with an expected true geometric means ratio 88.00%. Note that based on historic data from protocol SYN023-002 the geometric ratio from Study Day 42 through Study Day 112 is stable and therefore it is expected that a true ratio of 88.00% is reasonable to determine non-inferiority at Study Day 99.

7.8.3 Non-inferiority of Percentage of Subjects with Serum RVNA ≥ 0.5 IU/mL on Study Day 99

20 % margin of noninferiority was selected since it is a recommended bioequivalence margin for a lower bound of 0.8 (FDA 2001). Historical SYN023 data is presented In Table 7.8.3-1.

Table 7.8.3-1 Historical Percentage of Subjects with RVNA ≥ 0.5 IU/mL

DAY	SYN023 + Vaccine		RIG + Vaccine	
	≥ 0.5 IU/mL Count (percentage)	Total	≥ 0.5 IU/mL Count (percentage)	Total
0	3 (4.0%)	75	1 (1.3%)	76
1	67 (90.5%)	74	1 (1.3%)	75
3	74 (98.7%)	75	1 (1.3%)	76
7	75 (100.0%)	75	6 (7.9%)	76
14	75 (100.0%)	75	75 (98.7%)	76
28	75 (100.0%)	75	76 (100.0%)	76
35	74 (100.0%)	74	74 (100.0%)	74
42	73 (100.0%)	73	76 (100.0%)	76
84	72 (100.0%)	72	75 (100.0%)	75
112	70 (95.9%)	73	75 (98.7%)	76

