4.3.3. As-Treated Population (Safety Population)

Since post-exposure treatment of rabies is urgent and should not be delayed, randomization and prophylaxis will begin after a screening event that includes informed consent and survey of inclusion criteria before some exclusion criteria have been confirmed. High-risk bite victims that meet all initially knowable inclusion/exclusion criteria will be randomized to receive study drug and begin a regimen of rabies vaccination. All subjects who are randomized and receive study drug are included in the “As-treated” Population. Unless otherwise specified, summaries of adverse events, treatment compliance, laboratory results, and vital signs will be based on the As-treated Population grouped by actual treatment received and overall.

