7.2.2. Treatment Compliance and Modifications

Compliance will be summarized for rabies vaccinations. Treatment compliance is defined as the ratio of total number of vaccinations to the planned number of vaccinations, in terms of percentage. Treatment compliance will be summarized descriptively for both the As-treated and the Per-protocol Populations.

8. Efficacy Analysis

The primary and secondary efficacy endpoints may be performed on the As-treated and the Per-protocol Populations. The Per-protocol analyses will be considered primary; the As-treated analyses will be considered supportive. The denominator for all percentages will be the number of subjects in that treatment within the analysis set of interest, unless otherwise specified.

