The alternative hypothesis (H_a) is that the SYN023 vaccine is non-inferior to HRIG by a 20% margin.

$$H_a: \emptyset = \frac{GMC_{SYN023}}{GMC_{HRIG}} > 0.8$$

The null hypothesis is:

$$H_0: \emptyset = \frac{GMC_{SYN023}}{GMC_{HRIG}} \leq 0.8$$

The null hypothesis will be rejected at a significance level of 2.5% ($\alpha = 0.025$) if the lower bound of the one-sided 97.5% confidence interval for the GMC ratio is greater than the non-inferiority bound 0.8. Descriptive statistics will be displayed in a summary table following the same presentation for Section 8.1.1.1.

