8.1.2. Sensitivity Analyses

The as-treated analyses will be performed for the four elements of the primary analysis as the sensitivity analyses.

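### The supportive as-treated Day 99 GMC ratio pools previously vaccinated with naive subjects without adjusting for Day 1 serostatus, a modest and avoidable loss of precision

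*SAP*

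**What the plan says.** The as-treated set has no condition on Day 1 RVNA. SAP 4.3.3 reads: "All subjects who are randomized and receive study drug are included in the" As-treated Population. SAP 4.3 gives the set its role: "The As-treated Population will be applied on the primary endpoints as sensitivity analyses". SAP 8.1.2 sets the scope: "The as-treated analyses will be performed for the four elements of the primary analysis as the sensitivity analyses". The opening of SAP section 8 ranks it: "The Per-protocol analyses will be considered primary; the As-treated analyses will be considered supportive".

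The estimator in SAP 8.1.1.1 is a plain geometric mean per arm ("GMC for a group of subjects is calculated by multiplying all values and taking the" n-th root), compared as a ratio. SAP 8.1.1.2 uses the same estimator at Day 99 and declares non-inferiority if the "lower bound of the one-sided 97.5% confidence interval for the GMC ratio is greater than the non-inferiority bound 0.8". No covariate, stratum or subgroup based on Day 1 RVNA is named for any RVNA analysis. The fold-increase statistic in SAP section 12 falls under immunology other than PK and PD and carries no testing.

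Protocol 1.6 expects 2% to 5% of subjects to have unknown or unrecalled vaccination and a response that may be much faster and higher than in naive subjects. It says of an RVNA of 0.1 IU or more: "that is taken to be evidence of previous vaccination must be analyzed differently". SAP 5.2 lists that finding as a reason for exclusion from the per-protocol populations. Protocol Tables 3-1 and 3-2 require the Day 1 sample before Study Drug.

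**The concern.** The as-treated rerun is the only planned check on whether post-randomization exclusions drive the per-protocol result. It restores a small group expected to respond to vaccine very differently, and does nothing to separate them.

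On the log scale a few booster-type responses add variance, and a chance excess in one arm moves the ratio. The two analyses could then disagree, or agree, for a reason unrelated to SYN023's effect on the vaccine response. Day 99 GMC is the element where this matters most, because the planned ratio lies close to the margin. Since the Day 1 value precedes dosing, adjusting for it brings in no post-randomization information.

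**Working it through.** **The plan's own figure.** Protocol 7.8.2 gives a total of 138 for Day 99 ("The sample size is calculated at 80% power with 20% margin of non-inferiority and equal allowance", one-sided 0.025, true ratio 0.88). Table 7.8-1 prints a CV of 17%. With s² = ln(1 + 0.17²) = 0.0285 and gap = ln(0.88/0.80) = 0.0953, n per arm = 2 × 0.0285 × (1.960 + 0.842)² / 0.0953² ≈ 49.2, rounded up to 50. The total is 100 (102 with the t distribution), not 138. The Day 112 inputs of Table 7.8.2-2 (0.8694 and 17.32%) give 136 to 138. That discrepancy is a separate matter; what is used here is the gap of 0.0953.

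**Spread.** The printed CV is not used as the between-subject spread, because 17% is close to the standard error of the historical log ratio (0.164 at Day 84, 0.172 at Day 112). The arm-level intervals in Table 7.8.2-1 give log SD = [ln(upper/lower)/2] × √n / t:
- Day 84: 1.12 (SYN023), 0.83 (HRIG); pooled 0.99.
- Day 112: 1.16 (SYN023), 0.93 (HRIG); pooled 1.05.

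**Inputs.** n = 184 per arm in the NRG (Table 2.3-1), before any missing Day 99 values. Prevalence p = 2% to 5%, so 7 to 18 of 368 subjects. k is the Day 99 ratio of seropositive to naive RVNA. The documents give no value, so a range is shown.

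**Shift from imbalance.** A net excess of d seropositive subjects in one arm shifts the log ratio by d × ln(k)/n. The net excess that equals the gap is 0.0953 × 184 / ln(k). The SD of the shift is ln(k) × √[2p(1−p)/n]. Chances are for a shift of at least the gap in either direction, from two independent Binomial(184, p) counts.

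| k | Net excess equal to gap | SD of shift, p = 2% / 5% | SD as share of gap | Chance of full-gap shift, p = 2% / 5% |
|---|---|---|---|---|
| 5 | 10.9 | 0.0235 / 0.0366 | 25% / 38% | 0.02% / 1.2% |
| 10 | 7.6 | 0.0336 / 0.0523 | 35% / 55% | 0.6% / 7.2% |
| 20 | 5.9 | 0.0437 / 0.0681 | 46% / 71% | 4.1% / 18.6% |
| 50 | 4.5 | 0.0571 / 0.0889 | 60% / 93% | 9.2% / 27.9% |

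At k = 10 the chance of at least a half-gap shift is 19% (p = 2%) to 40% (p = 5%). A one-SD excess in the HRIG arm takes 0.88 to 0.88 × exp(−0.0336) = 0.851, or 0.88 × exp(−0.0523) = 0.835. The same excess in the SYN023 arm takes it up to 0.910 or 0.927. If the arms are balanced the ratio hardly moves: 0.88^0.98 = 0.882 and 0.88^0.95 = 0.886, assuming no treatment difference among seropositive subjects.

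**Variance.** Variance ratio = 1 + p(1−p)(ln k)²/SD². At p = 3.5%, k = 10 and SD 1.05: 1 + 0.0338 × 5.302/1.1025 = 1.16. With CI factor = exp[1.97 × √(2 × variance/184)]:
- unadjusted: variance 1.1025 × 1.162 = 1.282, factor 1.26;
- adjusted: variance 1.1025, factor 1.24.

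**Scale.** At log SD 0.99 to 1.05 and 184 per arm, the standard error of the log ratio is 0.103 to 0.109. Ordinary sampling error is already larger than the gap.

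**The case against.** The strongest reply is that nothing needs correcting. The as-treated set takes all comers by design and also restores wrong doses, missed vaccinations and other deviations. Under randomization the unadjusted ratio is valid, and its interval already reflects the extra variance and the chance imbalance. The analysis is supportive, so no success decision turns on it. SAP 5.2 already tabulates significant deviations, this one included, in the As-treated Population, and SAP 11.2 lists individual RVNA values, so an imbalance could be traced. All of this stands, and it limits the point to precision and balance.

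Three stronger inferences are tempting and are not supported.
- **A reader might infer that the SAP breaches the protocol's statement about analyzing these subjects differently.** That statement sits under the rationale for per-protocol exclusion, where excluded subjects are to be analyzed outside the per-protocol population. Excluding them there while keeping them in the as-treated set fits that text.
- **A reader might infer that a few seropositive subjects would typically move the ratio by the whole gap.** The net difference between arms matters, not the number present. A full-gap shift takes about 8 net subjects at 10-fold and 6 at 20-fold.
- **A reader might cite the Day 0 imbalance in SYN023-002 (3/75 v 1/76, Protocol Table 7.8.3-1) as showing movement toward the margin.** Those counts use the 0.5 IU/mL cut, not 0.1. The excess was also in the SYN023 arm, which raises the ratio: 0.88 × 10^(0.040−0.013) = 0.94 at 10-fold.

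What survives is that a known prognostic value, measured before dosing, goes unused in the one check on the per-protocol result.

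**Conclusion.** The point holds as an optional improvement to the as-treated Day 99 GMC analysis. Leaving out Day 1 serostatus lets chance imbalance move that ratio, up or down, by a material part of the 0.88-to-0.80 gap under the 10-fold assumption; a full-gap move is uncommon. The gain in interval width is small.

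These sizes rest on the protocol's 2% to 5% prevalence, 184 per arm with Day 99 data, and an assumed k. The historical SDs may themselves include some seropositive subjects.

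A reader might go on to infer that the primary conclusion is at risk. It is not: the per-protocol set removes these subjects, provided the Per-protocol Adjudication Board applies the SAP 5.2 list (SAP 4.3.5 words the exclusion as permissive). Elsewhere the effect is minor. At Day 8, Protocol Table 7.8-1 expects a ratio above 10. For the responder ratio, historical rates of 96% to 100% at Days 84 and 112 would leave a seropositive stratum with almost no variation.

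**What to change.** In SAP 8.1.2, add an as-treated estimate of the Day 99 GMC ratio from a linear model of log RVNA on treatment and Day 1 serostatus (at least 0.1 v below 0.1 IU/mL), reported beside the unadjusted ratio. Show Day 99 RVNA for seropositive subjects by arm. The same adjustment at Day 8 is optional, and no stratified responder ratio is needed.

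The cost is one covariate in a supportive model and one small table. No new data are required, the primary analysis is unchanged, and the text can be fixed before unblinding.
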